5.4.3 Trial Stopping Rules

For the primary outcome, the group sequential method of Lan and DeMets will be used to characterize the rate at which the type I error is spent.¹¹² This method is flexible with regard to the timing of the interim analyses. Asymmetric stopping boundaries will be used. The upper boundary which describes the stopping rule for benefit will be based on 1-sided type I error of .025 and the Lan-DeMets generalization of the O'Brien-Fleming boundary. The lower boundary will be based on a less stringent stopping rule: 1-sided type I error of .05 and the Lan-DeMets generalization of the Pocock type boundary.

It is also planned to calculate conditional power given the observed data to date, and conditional on the future data showing the originally assumed design effect. If this conditional power is low (under 10 percent) the DSMC may consider termination for futility if the accrual rate is slow, with confidence that the Type II error is not greatly inflated.¹¹³

Specific stopping rules for the trial will be established for monitoring maternal, neonatal and child events relevant to pravastatin risk. For the maternal stopping rule, an occurrence of one of the following events will qualify:

- Serious Adverse Event of Special Interest (serious AESI; myositis, myopathy, rhabdomyolysis or serious liver injury as defined in Section 4.5).
- Non-serious AESI (myalgia or muscle weakness as defined in Section 4.5) that required repeat discontinuation of study medication (initial discontinuation, rechallenge, discontinuation again)

For the neonatal stopping rule the following event will qualify:

- Failed newborn ABR/OAE test

The BCC will continuously monitor these maternal and neonatal events and if there is an excess of women in the pravastatin group who have experienced one or more of the events such that the one sided nominal p-value of a Fisher's exact test is less than 0.05 or such that the lower 90% confidence bound of the relative risk exceeds 1.0 for larger sample sizes of 50 or more, will request that the DSMC review the

data immediately and make a determination on stopping or pausing the trial, or modifying the dose. Likewise if there is an excess of neonates who have failed their hearing tests, the same stopping criteria will apply.

For the child stopping rule, the following events will qualify:

- Cognitive or Motor Scale Score < 70 (2.5th percentile) from the Bayley Certified Scales of Infant Development 4 at 24 months age
- Total problems or syndrome scale score > 97th percentile (clinical range) from the Child Behavior Checklist at 24 months
- Hearing loss at 24 months of age

These childhood events will be monitored by the DSMC at their regular meetings or more frequently upon request once any children reach two years of age. The 1-sided Lan-DeMets generalization of the Pocock type with type I error of .05 will be used as a stopping rule.

It is recognized that any decision to terminate the study would not be reached solely on statistical grounds but on a number of complex clinical and statistical considerations.

5.5 *Reporting from the DSMC*

At the conclusion of each call or meeting, an open session will be held to report the recommendations of the DSMC to the NICHD MFMU Network Project Scientist (and the NHLBI Project Scientist if desired). If the recommendations are complex and/or if requested by the Project Scientist, the BCC will collaborate with the DSMC Chair and the NICHD representative to write a brief summary of the discussion and recommendations for presentation to the NICHD Director.

In addition the BCC will prepare

- 1) Within 2 weeks, a brief summary of trial status and DSMC recommendations for NIH and the clinical centers including whether the trial should proceed or not, and whether modifications are required.
- 2) Within 4 weeks, detailed formal minutes of the DSMC's discussion and recommendations to the NICHD within 30 days of the meeting. The minutes are initially reviewed by the DSMC Chair, and then distributed to the members for final review and approval.
- 3) Within 4 weeks, a summary report for the IRB which will include a brief accounting of all adverse event reports since the previous meeting and cumulatively. If there are no safety or other protocol-related concerns, the report will state that the DSMC recommended that the study continue without modification. If concerns are identified, the report will outline the concerns and recommendations, as well as any decisions of the NICHD Director.

6 Statistical Considerations

6.1 Data Relevant to the Primary Outcome

To determine the recurrence rate of preeclampsia based on the gestational age at delivery of the previous preeclampsia, several sources of information were considered.

First, the NICHD MFMU Network conducted a randomized controlled trial to evaluate the efficacy of low dose aspirin compared with placebo in preventing preeclampsia in high-risk women. The trial, which was negative, included four independently powered arms, with one being in women who had prior preeclampsia, without other risk factors.⁴² One hundred sixty nine women who had a prior pregnancy complicated by preeclampsia that required preterm delivery were assigned to low dose aspirin, and had a rate of preeclampsia recurrence of 16% (27/169 women, 95% confidence interval 10%-22%).

The second source was a large cohort study in the US that included 6,157 women who had preeclampsia at the time of their first birth. In this study, the rates of recurrence of preeclampsia at their second delivery were 38.6%, 29.1% and 21.9% if the delivery for preeclampsia in the prior pregnancy occurred at 20-28 weeks, 29-32 weeks and 33-36 weeks, respectively.¹¹⁴ Assuming the same distribution of gestational ages at the index pregnancy as in the MFMU Network High Risk Aspirin trial the rate of recurrent preeclampsia before 34 weeks would be close to 31%.

An individual patient meta-analysis showed that the rate of recurrence of preeclampsia was 16.0% for women with prior preeclampsia (at any gestational age).¹¹⁵

In the VIP trial, women with prior history of preeclampsia with delivery < 37 weeks had a 23% recurrence rate of preeclampsia.¹¹⁶ In another study 25% of primiparous women who experienced preeclampsia and were delivered before 34 weeks, were diagnosed with preeclampsia in their next pregnancy.¹¹⁷

In a prospective cohort study using data from the Swedish medical birth register (763,795 women), Hernandez-Diaz and colleagues reported that for patients who had severe preeclampsia in their first pregnancy that required delivery before 34 weeks' gestation, the rate of preeclampsia recurrence was 29% in the subsequent pregnancy.¹¹⁸ Moreover, in the NICHD-OPRC pilot trials, which included women with history of preeclampsia that required delivery < 34 weeks, the rate of recurrence of preeclampsia in the placebo groups was 45%.⁹⁴

6.2 Sample Size and Power

In all of the older studies, except the High Risk Aspirin study, aspirin was not being used routinely. In the High Risk Aspirin trial, the dose was lower than is generally used today and was started later in gestation. Therefore, for the purposes of sample size estimation, it is conservatively assumed that all women will be receiving low dose aspirin, and that the rate of preeclampsia (primary outcome) in the placebo group is 20%. It is estimated that a sample size of 1,550 women is required to demonstrate at least a 30% reduction in preeclampsia with the use of pravastatin (from 20% to 14%), with a power of 85%, and type I error of 5% 2-sided. The sample size is adjusted for a drop-out rate of 5% (i.e. that 5% of the women on pravastatin discontinued their study drug and had the same primary outcome rate as the placebo group) and for the interim 'looks' at 50% and 75% information.

Table 5. Sample Sizes for Different, Levels of Power and Effect Sizes

Reduction in Primary Outcome Rate	Power %	Estimated Sample Size
25%	80	2000
	85	2280
	90	2660
30%	80	1360
	85	1550
	90	1810
35%	80	980
	85	1120
	90	1290

Trials evaluating cardiovascular disease event rates have reported that the combination of pravastatin and aspirin consistently has greater efficacy than pravastatin or aspirin alone indicating at least an additive and possibly a synergistic effect.¹¹⁹ Therefore, there is minimal concern that concomitant aspirin use would reduce the effect size.

Preterm birth < 37 weeks of gestation is considered to be the major secondary outcome. With a sample size of 1550, there is more than 80% power to detect an effect as small a 20% reduction in preterm birth.

The sample size for this study is also sufficient to detect with at least 80% power a 40% reduction in preterm delivery < 34 weeks and a 30% reduction in NICU/special care admission.

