Appendix A Design Summary

OBJECTIVE: To determine whether treatment with pravastatin among women with a prior history of preeclampsia with preterm delivery by 34 weeks reduce the rate of preeclampsia.

ORGANIZATION		SCHEDULED EVALUATIONS / DATA COLLECTION
Clinical Centers:	Magee, UAB, Ohio State, Utah, Brown, Columbia, Case Western, UT-Houston, UNC, Northwestern, UTMB-Galveston, U Penn	Pre-Randomization: 
❖ History❖ Dating ultrasound and AST/ALT if not done❖ BP, height, weight❖ Blood collection
Subcommittee:	[name] (Chair)	Randomization: 
❖ Blood collection at 23⁰ to 28⁶ and 33⁰ to 37⁶❖ Study visits monthly to assess side effects and AEs, record weight and BP, pill count and dispense study medication, review current medications
DESIGN		Post-randomization (monthly): 
❖ Delivery and neonatal data❖ Cord blood (first 50 participants)❖ Assess AEs and postpartum complications, record weight and BP
Major Eligibility Criteria:	
❖ Prior preeclampsia with delivery ≤ 34⁰❖ Gestational age 12⁰ to 16⁶ wks at randomization❖ Contraindications for statin therapy, use in current pregnancy	Maternal Follow-up at 2 yrs: 
❖ Medical history, BP, height, weight, waist and hip circumferences, blood collection
Groups:	
❖ Pravastatin 20mg❖ Matching placebo	Child Follow-up at 2 yrs: 
❖ Medical history, height, weight, vision & hearing assessment, neurodevelopment & behavior testing
Level of Masking:	
❖ Double masked	Child Follow-up at 5 yrs: 
❖ Medical history, height, weight, vision, neurodevelopment & behavior testing
Stratification:	
❖ Clinical site	
Sample Size:	
❖ 1550	
Assumptions:	
❖ Outcome = Incidence of preeclampsia❖ Placebo group event rate = 20%❖ Pravastatin group event rate = 14% (30% reduction)❖ Type 1 error = 5% 2-sided❖ Power =85%❖ Adjustment for 5% loss to follow-up and scheduled interim analysis❖ Lan-DeMets group sequential method	
Interim Analysis:		
TIMETABLE		
Enrollment:	
❖ Jun 2019 – Jul 2025	
Data collection:	
❖ Jun 2019 – Mar 2026 (primary)	

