Primary analysis:	
❖ Apr 2026 – Jun 2026 (primary)	
Child data collection:	
❖ Jun 2019 – Mar 2028 (child 2 yr follow-up)❖ Jun 2019 – Mar 2031 (child 5 yr follow-up)	
Closeout/final analysis:	
❖ Apr 2031 – Jun 2031	
MANAGEMENT PROTOCOL		
	Masked medication:	
❖ Daily dose of pravastatin 20mg or placebo until delivery
OUTCOME MEASURES		
	Primary:	
❖ Preeclampsia, mat death, or fetal loss < 20 wks
	Secondary:	
❖ Preterm birth < 37 weeks (major secondary)❖ Preterm birth < 34 weeks, gest age at delivery❖ Preeclampsia with severe features❖ Gestational hypertension❖ Gestational diabetes❖ Concentrations of angiogenic factors and lipids❖ Fetal and neonatal death❖ Birth weight and small for gestational age❖ Complications of prematurity❖ Child BMI for age at 2 and 5 years❖ Cognitive, Language and Motor Scale Scores from the Bayley 4 at 2 years❖ General Conceptual Ability score and subscale scores from the Differential Ability Scales at 5 years of age

References

1. American College of Obstetricians and Gynecologists. Hypertension in pregnancy; Report of the American College of Obstetricians and Gynecologists' Task Force on Hypertension in Pregnancy. *Obstet Gynecol* 2013;122:1122-31.

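### Is the 85% power for 1,550 women wrong because the 5% allowance and the 20% placebo rate are labelled in two ways?

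*Combined protocol and SAP*

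**What the plan says.** Section 6.2 gives the headline figure: "It is estimated that a sample size of 1,550 women is required to demonstrate at least a 30% reduction in preeclampsia". It sets the design values: two-sided type I error 5%, power 85%, and an assumption that "the rate of preeclampsia (primary outcome) in the placebo group is 20" percent, falling to 14% on pravastatin. It says the total of 1,550 already allows for the two interim looks and for 5% drop-out, which it spells out as the case where "5% of the women on pravastatin discontinued their study drug and had the same primary outcome rate as the placebo group". Table 5 gives nine sample sizes under the column heading "Reduction in Primary Outcome Rate".

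The assumptions list in Appendix A describes the same allowance as "Adjustment for 5% loss to follow-up and scheduled interim analysis" and the outcome as "Outcome = Incidence of preeclampsia". The outcome list in the same appendix gives the primary outcome as "Preeclampsia, mat death, or fetal loss < 20 wks". This matches the composite in 4.6.1.

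Section 6.3 analyses women as randomized regardless of compliance. It leaves women lost to follow-up out of the primary analysis and expects very few of them. Section 5.4.2 has the DSMC examine the design assumptions and the placebo primary outcome rate once the first 310 women have delivered, and advise on the sample size.

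**The concern.** Discontinuation and loss to follow-up are different adjustments. A woman who stops the drug stays in the analysis and dilutes the effect. A woman lost to follow-up leaves the analysis and reduces its size. One 5% cannot be both, and the two readings give different power.

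On the 6.2 reading the stated 85% also looks slightly high, and the gap has the same sign in every cell of Table 5. The rates reviewed in 6.1 are for recurrent preeclampsia, whereas the endpoint tested also counts maternal death and fetal loss before 20 weeks. It is therefore fair to ask which of the two the 20% describes.

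If the trial were materially underpowered, or if the DSMC did not know what to compare with 5% and 20% at the 310-delivery review, the plan would need correcting.

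**Working it through.** **Inputs.** Placebo 20%, pravastatin 14%, two-sided alpha 0.05, power 85%, N = 1,550 and looks at 50% and 75% (6.2); 1:1 allocation (3.6); comparison of two proportions (6.3); Lan-DeMets O'Brien-Fleming-type benefit boundary at one-sided 0.025 (5.4.3). The harm boundary is left out because it would rarely be crossed under a 30% benefit.

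**Looks.** Boundaries at 50%, 75% and 100% information are 2.963, 2.359 and 2.014. At 85% power they inflate N by 1.019.

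**No adjustment.** Unpooled formula: N = 2 × [p1(1−p1) + p2(1−p2)] × (1.960 + 1.036)² / (p1−p2)²
= 2 × (0.1600 + 0.1204) × 8.978 / 0.06² = 1,399. The Fleiss (pooled-null) formula gives 1,406.

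**Meaning in 6.2 (discontinuation).** Pravastatin rate = 0.95 × 14% + 0.05 × 20% = 14.3%.
- N = 2 × (0.1600 + 0.1226) × 8.978 / 0.057² = 1,562; Fleiss 1,568.
- With looks: 1,562 × 1.019 = 1,591; Fleiss 1,598. That is 41 to 48 women, or 2.7% to 3.1%, above 1,550.
- Power at 1,550 without looks: standard error √(0.2826/775) = 0.01909; 0.057/0.01909 = 2.985; 2.985 − 1.960 = 1.025, giving 84.7%.
- Power with looks: 84.1% (83.9% pooled).

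**Meaning in Appendix A (loss to follow-up).** About 1,472 women analysed, 20% against 14%.
- N = 1,399/0.95 × 1.019 = 1,500; Fleiss 1,508.
- Power at 1,550: 86.7% without looks, 86.1% with looks (85.9% to 86.0% pooled).

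**Where 1,550 may come from.** Two standard shortcuts reach it, one for each meaning of the 5%, and neither includes the looks:
- the unpooled N with a squared allowance, 1,399/0.95² = 1,550;
- the continuity-corrected N with a simple allowance, 1,472/0.95 = 1,549.

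Neither reproduces Table 5. The first gives 2,678 where the table has 2,660, and 969 where it has 980. The second gives 1,989 where the table has 2,000, and 1,301 where it has 1,290. The method actually used therefore cannot be identified from the documents.

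**Sensitivity.** On the 6.2 meaning with looks, a placebo rate of 20.5% instead of 20% gives 85.1%. A 30.5% reduction instead of 30% gives 85.3%.

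**Precision at the 310-delivery review.** With about 155 placebo women, the standard error of a 20% rate is √(0.2 × 0.8/155) = 3.2 points.

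**The case for a change.** The strongest case for acting has three parts.

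**The gap is systematic.** On the 6.2 meaning with looks, every Table 5 cell falls 0.6 to 1.1 points below its stated power. On the Appendix A meaning every cell falls above it, at 81.1 to 81.7, 85.9 to 86.5 and 90.6 to 90.9. This is correct, and it suggests that one step, perhaps the looks, was approximated or left out. It amounts to only 2% to 4% of N, and restating 79, 84 and 89 would replace an unseen calculation with a reviewer's own.

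**The DSMC needs clear benchmarks.** It does, but 5.4.2 names the placebo primary outcome rate as the quantity to examine, and 4.6.1 defines that outcome. Losses to follow-up and participant compliance are both on the DSMC's list in 5.1.3. The report in 5.4.1 covers compliance and data completeness, and the committee may ask for more, such as a breakdown by component.

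**The 20% may mean preeclampsia alone.** If so, fetal loss adds to it, and the documents give no rate for that loss. With an assumed 1% to 2%, power would be about 80% to 82% if the drug leaves loss unaffected, and about 86% to 88% if the 30% reduction covers the whole composite. These figures fall on both sides of 85% and rest on an outside assumption. Section 6.2 puts the primary outcome in brackets beside the 20%, and Table 5 and 6.3.1 use it in that sense, so the composite is the natural reading.

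What stands is the conflict over the 5% between 6.2 and Appendix A, together with loose shorthand for the outcome.

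**Conclusion.** The concern does not call for a change. The stated 85% is reproduced to within about one power point under either meaning of the 5%: 83.9% to 84.1% on the 6.2 meaning and 85.9% to 86.1% on the Appendix A meaning. The difference is about what half a point in the placebo rate would produce, and the recurrence rates cited in 6.1 run from 16% to 45%.

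The Appendix A wording is a clerical slip. Section 6.2 is the detailed text and defines its term, and 6.3 settles how both women who stop the drug and women lost to follow-up are analysed, whatever the 5% was meant to be. Calling the outcome preeclampsia is shorthand that 4.6.1 and the outcome list in Appendix A resolve. Tidying these labels would alter no sample size, test, boundary or conclusion.

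This rests on O'Brien-Fleming-type spending at the stated looks, on leaving out the harm boundary, and on reading the 20% as the composite rate.

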6.3 Analysis Plan

All statistical analyses will be based upon the total cohort of patients randomized into the trial. Although data on some patients may be missing, all relevant data available from each patient will be employed in the analyses. Patients will be included in the treatment group to which they were randomly assigned regardless of compliance.

The primary analysis will consist of a simple comparison of binomial proportions. The relative risks and confidence intervals will be reported. If the treatment groups are found to differ on a pre-treatment factor known to be a risk factor for the outcome, the statistical analysis will adjust for these differences, using a log binomial regression (or log-Poisson when relevant). An evaluation of treatment by center interaction will be included, using the Breslow-Day test. An analysis adjusting by center also will be performed to ensure that center differences do not change the conclusion.

If the primary outcome is significant or the trial is stopped early for benefit, the methods of Maurer and Bretz will be used to test formally the major secondary endpoint of preterm delivery < 37 weeks, while controlling the familywise error rate.¹²⁰

Loss to follow-up will be defined as the inability to ascertain whether a woman has preeclampsia. Those defined as lost to follow-up will not be included in the primary analysis. It is expected that the loss to follow-up rate will be very low. However, a sensitivity analysis will be performed including patients lost to follow-up with different assumptions regarding their outcome, to determine whether the results are

robust. Multiple imputation techniques (or a Bayesian bootstrap technique if the ‘missingness’ is non-ignorable) will be evaluated if required.¹²¹

Since many of the secondary endpoints are dichotomous variables like the primary outcome, standard statistical methods for rates and proportions will be appropriate. For normally distributed continuous outcomes, least squares means general linear regression will be used to estimate means and 95% confidence intervals. The Wilcoxon test and the Hodges-Lehmann estimators will be used to compare non-normal continuous variables that cannot be transformed to approximate normality. For time-to-event variables, the log-rank test and Cox proportional hazards model will be used (model assumptions tested by Lin’s test).

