2.1 Introduction

Preeclampsia is a pregnancy-specific syndrome characterized by widespread endothelial damage in multiple organ systems in the second half of pregnancy. Clinical presentation includes hypertension, proteinuria, and end organ dysfunction.¹ For the mother, preeclampsia may lead to seizure, stroke, intracranial bleeding, uncontrolled hypertension, renal failure, pulmonary edema, and death. For the fetus, it may lead to intrauterine growth restriction, death, and complications of prematurity.¹ Apart from the use of low dose aspirin, which remains controversial, there is no effective prophylactic therapy, and delivery remains the main approach to preventing maternal morbidity and mortality. However, this is frequently achieved at the expense of premature delivery and the associated neonatal morbidities and mortality. Women with underlying hypertension, pregestational diabetes, multifetal gestation, renal or autoimmune disease are at increased risk. Women with a previous history of preeclampsia, especially if early and severe, are at a substantially high risk (up to 65%) for the disease.^{1,2}

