3.6 Randomization Method and Masking

Consenting women will be assigned to pravastatin or placebo in a 1:1 ratio according to a randomization sequence prepared and maintained centrally by the Biostatistical Coordinating Center (BCC). The two study medication arms of the study (pravastatin or placebo) are double masked; neither the patient nor the clinical staff will be aware of the treatment assignment.

The simple urn method will be used to generate the randomization sequences because it provides a high probability of balance in treatment assignments, it is unpredictable, and it allows an explicit randomization analysis to be conducted with relative ease.¹⁰³ Randomization will be stratified by clinical site to assure balance between the two treatment groups with respect to anticipated differences among the clinic population and possible differences in patient management.

4 Study Procedures

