6.3.1 Subgroup Analyses

If the two groups show a difference in the incidence of the primary outcome or major secondary outcome, interactions will be evaluated and subgroup analyses conducted to determine whether the effect prevails throughout particular subgroups of patients. Indeed, NIH guidelines require investigators to evaluate consistency between the genders and across racial subgroups. It should be noted, however, that subgroup analyses have been greatly abused, particularly when there is no overall treatment difference.¹²² There is a strong temptation to search for a specific subpopulation in which the therapy is nevertheless effective. Yusuf et al. concluded “*the overall ‘average’ result of a randomized clinical trial is usually a more reliable estimate of the treatment effect in the various subgroups examined than are the observed effects in individual subgroups.*”¹²³ Thus subgroup analyses will be interpreted with care.

It is generally acknowledged that subgroup analysis that is pre-specified in the protocol has more validity than ad-hoc comparisons. The following factors will be considered for subgroup analysis, if there is a significant interaction between the factor of interest and the treatment effect:

- Race/ethnicity
- Baseline BMI category
- Gestational age at randomization
- Actual or prescribed aspirin use at baseline
- Pregestational diabetes
- Chronic hypertension at baseline
- Singleton pregnancy

For subgroup analyses, there will be more limited power. However, if an interaction test were positive for the primary outcome, indicating the presence of heterogeneity between subgroups, and 1) the subgroups were each 50% of the sample size and 2) the placebo outcome rate in the subgroup were the same as assumed overall (20%), then there would be more than 85% power to detect a 40% difference between treatment groups within one of the subgroups.

The racial/ethnic composition of women recruited into the MFMU Network trials varies. Assuming for this trial that the composition is 31% African-American and 24% Hispanic (estimates based on site specific rates reported among preeclamptics in the RCT of Antioxidants to Prevent Preeclampsia CAPPs trial) there is more than 85% power to detect a 50% reduction in the primary outcome in African American women and 77% power to detect a 50% reduction in the primary outcome in Hispanic women within these separate subgroups.

7 Data Collection

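### The primary comparison is valid but unadjusted; a pre-specified model using baseline factors already collected would gain from nil to about 2.6 power points at the same 1,550 women

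*Combined protocol and SAP*

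**What the plan says.** **Primary test.** Section 6.3 states: "The primary analysis will consist of a simple comparison of binomial proportions". Results are reported as relative risks with confidence intervals.

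**Site.** Section 3.6 states: "Randomization will be stratified by clinical site to assure balance between the two treatment groups". In Section 6.3 site appears only in a treatment-by-center interaction test and in a supporting analysis: "An analysis adjusting by center also will be performed to ensure that center differences do not change the conclusion".

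**Other covariates.** These enter conditionally: "If the treatment groups are found to differ on a pre-treatment factor known to be a risk factor for the outcome", a log-binomial or log-Poisson regression is to adjust for the difference. Section 6.3 gives no covariate list and no criterion. It does not say whether the adjusted result replaces the primary one.

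**Known risk factors.** Section 2.1 states: "Women with underlying hypertension, pregestational diabetes, multifetal gestation, renal or autoimmune disease are at increased risk". Section 6.3.1 lists "Chronic hypertension at baseline", "Pregestational diabetes" and "Singleton pregnancy" as subgroup factors. Section 6.1 cites recurrence of 38.6% when the earlier delivery was at 20-28 weeks and 29.1% at 29-32 weeks. Section 3.4.1 requires the qualifying delivery to be documented, and Section 4.3 collects chronic disease history and the outcomes of all earlier pregnancies.

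**The concern.** Adjusting for baseline factors that predict the outcome narrows the interval for the treatment effect without enrolling anyone else. The usual practice is also to carry the stratification factor into the analysis. Here the stratum and several predictors that the protocol itself names are left out of the deciding test. At stake is a small amount of power, in a trial whose power with the planned looks is close to, and slightly below, its 85% target.

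A smaller point of wording goes with this. The conditional-adjustment sentence leaves unstated which result is compared with the Lan-DeMets boundaries (Section 5.4.3) and which opens the test of preterm birth before 37 weeks. Because the unadjusted test is labelled primary, the natural reading is that it decides.

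**Working it through.** **1. The plan's own figure.** Section 6.2 gives 20% against 14%, 5% drop-out to the placebo rate, two-sided 5%, 85% power, and looks at 50% and 75%.
- Diluted pravastatin rate: 0.95 × 14% + 0.05 × 20% = 14.3%, so RR = 0.143/0.20 = 0.715.
- n per arm = (1.960 + 1.036)² × (0.20 × 0.80 + 0.143 × 0.857) / (0.057)² ≈ 781, or 1,562 in total (1,568 with pooled variance).
- Group-sequential inflation of 1.019 gives 1,592 (1,598 pooled). The stated 1,550 is within about 3% of these.
- Power at 775 per arm is 84.6% without looks and 83.9% with looks (bounds z = 2.963, 2.359, 2.014). The plan's figure is reproduced.

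**2. What the documents say about covariate strength.** Only index gestation has a figure: odds ratio (0.386/0.614)/(0.291/0.709) = 1.53. Everything else is assumed:

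| Setting | Site SD (logit) | Chronic hypertension | Diabetes | Twins |
|---|---|---|---|---|
| C, weak | 0.15 | 20%, OR 1.5 | 10%, OR 1.5 | 4%, OR 1.5 |
| A, moderate | 0.3 | 30%, OR 2 | 10%, OR 2 | 4%, OR 2.5 |
| B, strong | 0.5 | 30%, OR 3 | 10%, OR 2 | 4%, OR 2.5 |

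In all settings 35% of women are assumed to have an index delivery at 20-28 weeks. Each setting was run with 12 sites (the twelve centers of Section 8.1) and with 30. The larger number is tried because Section 4.8 distinguishes a center's PI from a site PI, so there may be more strata than centers.

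**3. Simulation.** The design was 1,550 women, looks at 775/1,162/1,550, urn randomisation within site, placebo rate 20%, constant RR 0.715 and 6,000 trials per cell. The adjusted model is log-link Poisson with robust variance multiplied by n/(n-k), k being the number of parameters. Power (%) with looks, Monte Carlo SE 0.5:

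| Sites | Setting | Unadjusted | Site only (Mantel-Haenszel) | Full model, corrected |
|---|---|---|---|---|
| 12 | C | 84.1 | 84.0 | 84.2 |
| 12 | A | 84.5 | 84.6 | 85.2 |
| 12 | B | 82.6 | 83.2 | 85.2 |
| 30 | C | 83.6 | 83.1 | 83.4 |
| 30 | A | 84.2 | 84.4 | 85.0 |
| 30 | B | 83.8 | 84.5 | 85.5 |

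Taking differences before rounding, the full model gains nothing in C, 0.7 to 0.8 point in A and 1.8 to 2.6 points in B. Site alone gives -0.4 to +0.7.

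**4. Precision.** The information gain is the squared ratio of empirical SDs of log RR. For A with 12 sites it is (0.1137/0.1124)² = 1.023, and for B (0.1133/0.1110)² = 1.042. Over both site numbers the gain is 0.2-0.6% in C, 1.5-2.3% in A and 3.4-4.2% in B. From A to B that equals 0.015 × 1,550 ≈ 23 to 0.042 × 1,550 ≈ 65 women. Without index gestation the gains are 0.9-1.9% (A) and 3.0-4.0% (B).

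**5. Type I error.** Two-sided (Monte Carlo SE 0.3): unadjusted 4.4-5.8%, full corrected model 4.7-5.6%, conditional-adjustment rule 4.3-5.5%. If that rule is triggered at p < 0.05 on any of four factors, it should fire in about 1 - 0.95⁴ = 18.5% of trials. It fired in 18-19% and changed the verdict in 0.8-1.2% of all trials.

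**6. Early looks.** With 30 sites at the 50% look, the uncorrected robust SE is 2.8-3.7% too small. The factor √(775/740) = 1.023 reduces this to 0.5-1.4%. False benefit crossing at that look is 0.12-0.20% with the corrected model, against a nominal 0.15%.

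**7. Cross-checks.** A separate simulation using logistic standardisation and other assumed strengths gave gains of 0.5, 1.5 and 2.6 points. A fixed-sample simulation with 12 sites and corrected variance gave 0.3, 1.1 and 1.8. A repeat of setting B with 12 sites (7,200 trials) gave 2.2 (SE 0.3).

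**The case against.** The strongest reply is that this is a preference. The unadjusted test holds its level, the trial was sized for it, and Section 6.3 already plans a center-adjusted analysis and adjustment for imbalanced risk factors. That stands, and it is why the point is only an efficiency suggestion.

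The size of the gain is also open to challenge:
- No section gives a prevalence or odds ratio for hypertension, diabetes or twins, or a between-site spread. Thirty sites is an inference.
- The 35% share at 20-28 weeks fits Section 6.1 poorly. With two bands, its pooled figure of about 31% implies (31 - 29.1)/(38.6 - 29.1) = 20%.
- The odds ratio of 1.53 excludes women delivered at 33 to 34 weeks, who are eligible.
- The constant relative risk in the simulation suits a log-link model.

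These limit how exact the figures are. They do not reverse the direction, and the gains without index gestation show that little hangs on that covariate.

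Stronger readings are tempting:
- A reader might infer a gain of 3 points or more. Without the variance correction the strong setting does give 2.4 to 2.9. Scaling variance by (1 - R²) with R² of 10% would suggest 83.9% to 87.5%. But the recommended analysis carries the correction, and an R² of 10.1% cut the simulated variance under the alternative by only 5.0%.
- A reader might infer that ignoring the stratum, or the conditional-adjustment sentence, distorts type I error. The results above do not show that.
- A reader might take the omission of site as the main loss. It contributes almost nothing.

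**Conclusion.** The point holds as an optional improvement. At 1,550 women, a pre-specified adjusted analysis is worth between nothing and about 2.6 power points, depending on covariate strengths that the documents do not give. Nearly all of the gain is due to the clinical covariates. In the moderate and strong settings it brings power with the looks to 85.0-85.5%, the level Section 6.2 aims for. Type I error remains near 5% with or without the change. The documents do not support calling the planned test invalid or the sample size wrong.

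**What to change.** Before any primary-outcome result by arm is seen, amend Section 6.3 along these lines:

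- The primary analysis is the relative risk from a log-link Poisson model with robust variance multiplied by n/(n-k). It is adjusted for clinical site, chronic hypertension, pregestational diabetes, singleton or twin pregnancy, and gestational age at the qualifying delivery (20-28 weeks against 29 weeks or later; the earliest if there is more than one).
- Site grouping is fixed once for all looks, for example the twelve clinical centers or one pre-specified pooling rule. Pooling afresh at each look would change the model: with 30 sites, an average of 13.7, 8.0 and 4.2 sites had fewer than 20 women at the three looks. Pooling itself changed power by at most about 0.2 point.
- A missing covariate is handled by a simple stated rule, such as assigning the most frequent category with both arms combined, so that every randomised woman with a known outcome is kept. This is needed because Section 3.4.1 requires proof of delivery by the limit, not the exact week.
- The same model is used at both interim looks and the final look against the Lan-DeMets boundaries, and it opens the preterm-birth test.
- The unadjusted comparison becomes a sensitivity analysis. The conditional-adjustment sentence is deleted or labelled supportive.

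Renal and autoimmune disease are left out: Section 6.3.1 does not list them, and Section 3.4.3 excludes chronic renal disease with creatinine at or above 1.5 mg/dL.

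If the unadjusted test stays primary, one clause is enough: it meets the boundaries and opens the preterm-birth test, and any triggered adjustment is supportive.

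**Cost.** The change is an amendment to protocol Section 6, which under Section 1.3 needs Steering Committee and single-IRB approval and submission to the IND, plus a little more analysis work. The sample size and data collection are unchanged.
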